OBSERVATIONAL STUDY WITH ADDITIONAL DIAGNOSTIC PROCEDURES ON ANTI-TAT IMMUNE RESPONSE IN HIV-1-INFECTED HAART-TREATED ADULT SUBJECTS

Protocol Number: ISS OBS T-002

Study sponsored by

Istituto Superiore di Sanità

Data collection and analysis

National AIDS Center Istituto Superiore di Sanità [name]

LIST OF CLINICAL SITES AND PRINCIPAL INVESTIGATORS:

Ospedale A. di Savoia Prof. [name] [name]

Ospedale S. Raffaele Prof. [name]/[name] [name]

Ospedale Sacco Prof. [name] [name]

Policlinico di Modena Prof. [name] [name]

Spedali Civili Prof. [name] [name]

Ospedali Riuniti Prof. [name] [name]

Arcispedale S. Anna Prof. [name] [name]

Ospedale S. Maria Annunziata Prof. [name] [name]

IFO-San Gallicano Prof. [name] [name] AIDS National Center- ISS Observational Protocol ISS OBS T-002 Version date 14/06/2007

CONFIDENTIAL

INMI "L. Spallanzani" Prof. [name], Prof. [name] [name]

Ospedale S.M. Goretti Prof. [name] [name]

Policlinico di Bari Prof. [name] [name]

OBSERVATIONAL STUDY WITH ADDITIONAL DIAGNOSTIC PROCEDURES ON ANTI-TAT IMMUNE RESPONSE IN HIV-1-INFECTED HAART-TREATED ADULT SUBJECTS

Protocol Number: ISS OBS T-002 Date: June 14, 2007

PROTOCOL SUMMARY

Protocol :	A prospective observational study on the clinical, immunological and virological outcome of HAART-receiving HIV-1 infected adult subjects. The primary endpoint of this study is to evaluate the frequency, magnitude, quality and persistence of the anti-Tat humoral and cellular immune response in HIV-1 infected individuals under successful HAART. The secondary endpoint is to prospectively evaluate the immunological, virological and clinical outcome of anti-Tat positive versus anti-Tat negative subjects under successful HAART in order to define novel prognostic markers for the clinical management of HIV-1 infected HAART-treated subjects. In addition, the study will promote the creation of a network of clinical centers working according to standard operating procedures for the harmonization of the conduction of future vaccine trials.
Subjects:	HIV-1 infected adult subjects of either gender, ≥ 18 years old, under successful HAART (chronic suppression of HIV infection with a plasma viremia <50 copies/ml in the last 6 months and without a history of virologic rebound) and a known nadir level of CD4 ⁺ T cells.
Number of subjects:	Enrollment will be open to all HIV-1 infected adult subjects under HAART regimens at the participating clinical centers.
Time Period:	5 years with possibility of extension.
Sponsoring Agency:	Istituto Superiore di Sanità (ISS) [name]

1. PURPOSE OF THE STUDY

The present study is designed as a prospective observational study directed to evaluate the frequency, magnitude, quality and persistence (primary endpoint) of the anti-Tat immune response in highly active antiretroviral therapy (HAART)-receiving HIV-1 infected individuals, and to prospectively evaluate the immunological, virological and clinical outcome of anti-Tat positive versus anti-Tat negative subjects under successful HAART (secondary endpoint) in order to determine the impact of anti-Tat immunity on HIV disease progression as well as the potential use of anti-Tat immune response assessment for the clinical and therapeutic management of HAART-treated infected patients. This survey, that will evaluate a large number of subjects, will provide important information for the design, planning and conduction of future therapeutic vaccine trials based on the HIV-1 Tat protein in HAART-treated patients.

2. BACKGROUND AND RATIONALE

The HIV-1 Tat is a very early regulatory protein that plays a major role in HIV-1 replication and AIDS pathogenesis. Tat is produced early after infection, even prior to HIV integration, being necessary for viral gene expression (Arya, Science 1985; Fisher, Nature 1986; Ensoli, J Virol. 1993; Wu, Science 2001), cell-to-cell virus transmission and disease progression. Tat therefore represents a key HIV-1 target protein for the host immune response and an optimal candidate for the development of a vaccine against HIV/AIDS (Ensoli, Nature 1990, J. Virol. 1993, Nature 1994; Chang, AIDS 1997, Ensoli, AIDS 2006). Several studies suggest that in natural HIV infection an immune response to Tat (humoral and cellular) exerts a protective role upon disease progression. In particular, the presence of anti-Tat antibodies strongly correlates with a slower progression to the disease (Reiss, 1990; Rodman, 1993; Re, 1995; Zagury, 1998; Re, 2001; Rezza 2005). However, anti-Tat antibodies are produced by only a small fraction (around 20%) of asymptomatic HIV infected individuals while, in contrast, the majority (50% to 70%) of these individuals generates an adaptive y-IFN T-cell response against Tat, as well as a wide spectrum of antibodies against virtually all other virus components, including other regulatory gene products (Rev, Nef). This indicates the existence of a strong Th1 T cell response against Tat in asymptomatic HIV infection, as compared to the limited (frequency, titre and repertoire) anti-Tat Th2 B-cell response. In addition, most anti-Tat antibodies recognize only conformational Tat epitopes, and in most cases fail to recognize linear epitopes (Ensoli, AIDS 2006). Overall, the anti-Tat humoral response appears to be clustered in a fraction of asymptomatic HIV-infected patients (Stage A HIV disease) with peak frequencies in Long Term Non Progressor (LTNP) individuals (around 30 % to 40 %), and is lost in more advanced stages of the disease (Krone 1988, Demirhan 2000, Re 2001) as well as in fast progressors to AIDS (Zagury 1998). Results of a cross-sectional and longitudinal study recently performed in a cohort of 252 individuals with accurately estimated dates of seroconversion and a medium follow-up of 7.2 years, revealed a strong association between the presence of anti-Tat antibodies and a slower progression to overt disease (Rezza, 2005). In fact, the risk of developing AIDS or severe immunodeficiency was 60% lower for anti-Tat positive individuals than for anti-Tat negative individuals. The longitudinal analysis also indicated that none of the individuals who were persistently anti-Tat positive progressed to AIDS, whereas 53 events (AIDS or severe immunodeficiency) occurred among those who were persistently anti-Tat negative (Rezza, 2005). Thus, a strong correlation exists between the presence of anti-Tat antibodies and non-progression to AIDS. This suggests that the presence of anti-Tat antibodies may predict the clinical outcome and that the induction of an immune response against Tat either during the course of the natural infection or by vaccination, may contrast the progression to the disease. Thus, the anti-Tat immune

response represents an immune correlate of protection which may have an important prognostic value and direct implications for the clinical and therapeutic management of infected patients. This notion also suggests that therapeutic vaccination with a Tat-based vaccine should be targeted only at those individuals that do not develop a humoral immune response to Tat in the natural course of the infection. On this basis, the knowledge of the impact (and the potential for a reciprocal influence) that the implementation of different HAART regimens may exert upon the preservation or the generation of Ag-specific immune responses might be of critical importance in the clinical and therapeutic management of infected subjects as well as for therapeutic vaccine development. Although HAART usually induces a potent suppression of viral replication with a net improvement of immunologic parameters (i.e. sustained increases in CD4⁺ T cell number), very little is known about the characteristics of the adaptive immune response against Tat as well as other viral antigens during HAART. In addition, it is unknown whether the different class of antiretroviral drugs may play a part in influencing the quality of the immune reconstitution. Indeed, HIV protease inhibitors (HIV-PI) have been shown to interfere with the maturation and function of dendritic cells and cytotoxic T lymphocytes and to alter the apoptotic pathway of T cells and hematopoietic cell precursors (André, 1998; Schmidtke, 1999; Gruber, 2001; Kobayashi, 1999; Sloand, 1999 & 2000; Weichold, 1999; Lu & Andrieu 2000, Phenix, 2001). On the other hand, nucleoside reversetranscriptase inhibitors (NRTI) and non-nucleoside reverse-transcriptase inhibitors (NNRTI) have also been shown to interfere with the growth of hematopoietic cell precursors, T cells and peripheral blood mononuclear cells (Somadossi, 1987; Chitnis, 2002; Viora, 1995 & 1997; Pilon, 2002; Hashimoto, AIDS Res Hum Retrov 1997; Mangiacasale, 2003). Altogether, these data suggest that, by directly or indirectly interfering with cells of the immune system, all the different combination regimens of antiretroviral drugs may concur in altering the immune response in infected patients as well as potentially in vaccinees.

It is, therefore, of utmost importance to collect data on the frequency, magnitude, quality and persistence of the anti-Tat immune response in different cohorts of HIV-1 infected individuals under different HAART regimens. These data will be essential to prospectively evaluate the immunological, virological and clinical outcome of anti-Tat positive versus anti-Tat negative patients which are treated by different antiretroviral intervention, and to define the potential application of this novel immunologic analysis in the clinical staging and therapeutic management of infected patients. In addition, by creating a network of clinical centers working according to standard operating procedures (SOPs), identifying potential vaccinee's cohorts and simplifying all the pre-screening procedures for enrollment, this study will be key for the design and conduction of future therapeutic Phase II vaccine trials based on the HIV-1 Tat protein in HAART-treated subjects. In particular, the results of the Phase I Safety and Immunogenicity Trials of Recombinant HIV-1 Tat (ISS P-001 and ISS T-001) demonstrated that the vaccine based on the recombinant Tat protein is well tolerated and immunogenic in both seronegative (Preventative trial) and seropositive (Therapeutic trial) individuals. Based on these data, phase II therapeutic trials will be targeted on individuals with no detectable humoral immune response against Tat and will be conducted in parallel by two distinct multicentric studies, which are going to start soon in Italy and will address two different clinical categories consisting of patients undergoing HAART regimens and asymptomatic drug-naïve individuals respectively.

3. STUDY DESIGN AND OBJECTIVES

The goal of this observational prospective study is to collect information on the frequency, magnitude, quality and persistence of anti-Tat immunity in HIV-1 infected subjects under successful HAART, to evaluate the immunological, virological and clinical outcome of anti-Tat positive versus the anti-Tat negative HAART-treated subjects, and to define whether the assessment

of anti-Tat immunity in HAART-treated patients may prove useful for the clinical and therapeutic management of infected patients.

Since these evaluations require assessments that go beyond the routine clinical monitoring, this protocol represents an observational study with additional diagnostic procedures.

3.1 Primary endpoint

The primary endpoint of the study is to evaluate the frequency, magnitude, quality and persistence of the anti-Tat humoral and cellular immune response in HAART-receiving individuals with chronically suppressed HIV-1 infection. Patients will be stratified according to PI-based or NNRTI-based HAART regimens.

3.2 Secondary endpoint

The secondary endpoint of the study is to prospectively evaluate the immunological, virological and clinical outcome of anti-Tat positive versus anti-Tat negative subjects under successful HIV-PI- or NNRTI-HAART in order to define immunologic markers of potential prognostic value for the clinical and therapeutic management of the disease.

The aim of this study is also to create a network of clinical centers working according SOPs for the conduction of future vaccine trials and for the management of HIV-1 infected HAART-treated subjects.

3.3 Clinical and immunological determinations

The presence of specific humoral and cellular immune responses will be monitored by determining anti-Tat antibodies in the sera of subjects, and by assessing the proliferative response (CFSE) and the production of γ IFN, IL-4 and IL-2 (Elispot) by peripheral blood mononuclear cells (PBMC) in response to Tat. Refer to section 6 for details of the laboratory assays to be performed.

The decline of CD4⁺ T cell counts, the increase of HIV plasma viral load or the occurrence of AIDS-defining events will be assessed to determine disease progression.

3.4 Study population

Enrollment will be open to all HIV-1 infected adult subjects of either gender, under any HAART regimen with a known nadir level of $CD4^+$ T cells and chronically suppressed HIV infection (plasma viremia <50 copies/ml in the last 6 months and without a history of virologic rebound).

No sample size limitation is defined and the number of the subjects enrolled will depend on the accrual capability of participating clinical centers.

3.5 Selection criteria

Informed consent will be obtained prior to assessments of eligibility. Subsequently, investigators will proceed with medical history, physical examination, and blood collection for routinary and extra-routinary tests.

CONFIDENTIAL

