6.0 STUDY ASSESSMENTS

The following sections provide a detailed listing of the clinical, immunological and virological determinations to be performed in this protocol.

The visits, during which the clinical and laboratory parameters and biological samples necessary to conduct the study are collected, will adhere to the timing of routine clinical monitoring, therefore, visits are scheduled every 3 ± 1 months (see study schedule at section 6.5 for details).

Most of the immunological assessment included in the study is not performed at routine evaluation of the patients, however the amount of blood to be collected for the specific purposes of this study will be reduced to a minimum volume and will be performed, at least in part, on the same samples collected for routine patient monitoring, as detailed in section 6.3.

The first line of testing includes the minimal panel of assays required to identify the presence of an immune response to Tat, which correspond to the primary endpoint of the study; the second line of testing will allow a more detailed exploration of the immune response against Tat and will be performed according to specimens (PBMC, sera, plasma) availability. Following the same principle of "minimal necessary testing", the blood samples (other than those collected for routine clinical monitoring) required in this study will be scheduled every three months only during the first year of conduction of the study, and will be performed every six months thereafter.

SOPs for all these assays have been developed and validated within the FP6-AVIP European Community funded AIDS vaccine program and the Italian Concerted Action on HIV/AIDS Vaccine Development (ICAV), and were employed to determine the immunogenicity induced by the Tat-vaccine in phase I preventative (P-001) and therapeutic (T-001) clinical trials (Ensoli, 2006).

The aim of this study is also to contribute to the ongoing process of standardization, qualification and harmonization of the procedures already developed for future vaccine trials.

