The visits and clinical evaluations, which will follow the timing of routine clinical monitoring, are scheduled every 3 ± 1 months.

The immunological and virological assessments will be performed according to the same schedule during the first year of observation in order to fully characterize the patients. However, in the absence of signs of disease progression, the additional evaluations will be performed every 6 months during the second year of follow-up and thereafter.

VISITS SCHEDULE

			First Year				Second	Year *	
MONTH (±1)	0	3	6	9	12	15	18	21	24
STUDY VISIT	01	02	03	04	05	06	07	08	09
Signed Informed Consent	X								
Medical History	X								
Anti-Tat antibodies (IgG, IgM, IgA)	Х	X	X	X	X	X	X	X	X
Clinical Evaluations									
Physical examination	X	X	X	X	X	X	X	X	X
Hematology	X	X	X	x	x	Х	X	X	X
Blood chemistry	X	X	X	x	X	Х	X	X	X
Concomitant medications	X	X	X	x	X	Х	X	X	X
Immunological-Virological Evaluations									
Lymphocyte phenotype	X	X	X	x	X	Х	X	X	X
HLA typing	X								
CD4+ T cell count	Х	X	X	X	X	X	X	X	X
HIV-1 plasma viremia	X	X	X	x	X	X	X	X	X
Lymphoproliferative response	X	X	X	X	X		X		X
γ-IFN, IL-4, IL-2 production	X	X	X	x	X		X		X
PBMC, plasma and sera freezing	Х	X	X	X	X		х		X

(Visits for the third, fourth and fifth year of the study will be scheduled as for the second year)

* The serological assessment after the first year of the study will be performed on sera frozen obtained at each routine visit (about every 3 months), without additional blood withdrawals.

6.6 Statistical considerations

Sample size

For this observational study no sample size will be predefined due to the fact that the study has the objective of providing information about the frequency, magnitude, quality and persistence of the anti-Tat immune response and of the immunological, virological and clinical outcome in HAART-receiving HIV-1 infected individuals.

Primary variables

- Anti-Tat humoral immune response in terms of IgM, IgG, IgA anti-Tat antibodies
- Epitope mapping of IgM and IgG anti-Tat antibodies
- Neutralization of Tat activity by rescue assay
- Anti-Tat cellular-mediated immune response, in terms of lymphoproliferative response to Tat (CFSE staining), and in vitro γIFN, IL-4, IL-2 production in response to Tat (Elispot, Intracellular staining)

Secondary variables

- Change of CD4⁺ T cells and HIV viral load

- Trend over time of lymphocytes populations
- Time to AIDS defining clinical condition (according to the CDC criteria)

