Other immunological and virological evaluations will be performed and analyzed during the study period.

Statistical analysis

Anti-Tat humoral-cellular immune response will be evaluated by the percentage of anti-Tat positive subjects with the relative 95% confidence interval; geometric mean antibody titers (GMT) will be also performed.

The immune response will be compared between subjects groups stratified by NNRTI-based or PIbased HAART regimens, using a Logistic regression model (odds ratio estimates).

CD4⁺ T cells and HIV viral load will be evaluated and compared between anti-Tat positive and negative subjects using an Analysis of variance model (ANOVA).

The time to AIDS will be determined and compared between groups by the Log-Rank test.

A Multivariate analysis will be applied to the immunological and virological parameters in order to carry out potential prognostic factors for the clinical outcome.

Statistical analysis and data processing will be performed using SAS[®] software for Windows.

All descriptive statistics used to summarize numeric data will include mean values, standard deviation, median, minimum and maximum. Frequency distributions will be presented for categorical variables.

95% confidence intervals will be determined for all data.

All statistical tests will be performed at two-sided with a 5% significance level.

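### Time to AIDS is compared by log-rank between anti-Tat groups whose classification time is not fixed, and sections 6.0 and 6.5 disagree on whether testing frequency depends on progression

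*Protocol*

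**What the plan says.** Section 3.2 of the protocol sets the secondary endpoint: to "prospectively evaluate the immunological, virological and clinical outcome of anti-Tat positive versus anti-Tat negative subjects". Section 6.6 supplies the tests. CD4 count and viral load are compared between anti-Tat positive and negative subjects by ANOVA. Then: "The time to AIDS will be determined and compared between groups by the Log-Rank test". That sentence does not name its groups; read with 3.2 and with the ANOVA sentence, they are the anti-Tat groups. Positivity appears in 6.6 only in general terms: "Anti-Tat humoral-cellular immune response will be evaluated by the percentage of anti-Tat positive subjects with the relative 95% confidence interval". No visit is attached to it.

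The table and footnote in 6.5 schedule anti-Tat antibodies at month 0 and at every visit afterwards, about every 3 months, for all subjects. Persistence of the response is part of the primary endpoint (3.1). The background (section 2) reports from a cited seroconverter cohort that "none of the individuals who were persistently anti-Tat positive progressed to AIDS".

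On the additional evaluations, 6.5 says that "in the absence of signs of disease progression, the additional evaluations will be performed every 6 months during the second year of follow-up" and thereafter. Section 6.0 says that the extra blood samples "will be scheduled every three months only during the first year of conduction of the study, and will be performed every six months thereafter", with no reference to progression.

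**The concern.** A plain log-rank test is valid only if each subject's group is known when the clock starts. If a result obtained during follow-up decides the group, a subject who becomes positive in year 3 must have been free of AIDS until then. Those event-free years are credited to the positive group, which then looks protected even with no effect. The same holds for a persistent-positive group that requires a run of positive results. The stated use of the comparison is prognostic markers for clinical and therapeutic management (3.2), so a spurious association would matter.

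The second issue is data collection. Under 3.3, progression means CD4 decline, viral load increase or an AIDS-defining event, which largely coincide with the secondary outcomes. If progression keeps a subject on more frequent cellular testing, the chance of recording a cellular response depends on the outcome.

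**Working it through.** The protocol states no event count, power or effect for this comparison, so there is no figure to reproduce. The check asks what each permissible grouping gives when anti-Tat status has no effect.

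**Inputs from the protocol.** Follow-up F = 5 years (3.6). Tests every 3 months (6.5). About 20% antibody-positive (section 2, from asymptomatic infection in general, not specific to HAART). Two-sided 5% level (6.6).

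**Assumed, not in the protocol.** AIDS hazard h = 1% or 3% per year. Conversion from negative to positive c = 2%, 5% or 10% per year. N = 300 or 1000. No loss of antibody.

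**Closed form for ever- versus never-positive, per enrolled subject.** Let L = h + c.
- Never-positive events: En = 0.8 × (h/L) × (1 − e^(−LF)).
- Never-positive person-years: Pn = 0.8 × {h[1/L² − e^(−LF)(F/L + 1/L²)] + F e^(−LF)}.
- All subjects: events 1 − e^(−hF), person-years (1 − e^(−hF))/h.
- Ever-positive: all minus never-positive.

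Worked case, h = 0.01 and c = 0.05, so L = 0.06 and e^(−0.3) = 0.7408:
- En = 0.8 × 0.1667 × 0.2592 = 0.0346.
- Pn = 0.8 × (0.1026 + 3.7041) = 3.0454.
- All: 0.0488 events, 4.8771 person-years.
- Ever-positive: 0.0142 events, 1.8317 person-years.
- Rates: 0.00776 against 0.01135 per year. Ratio 0.68, although the true ratio is 1.

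**Null simulation of the log-rank test** (conversion detected at the next quarterly visit, 600 runs per setting):

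| Conversion per year | Closed-form rate ratio | Log-rank hazard ratio, ever-positive | Type I error, ever-positive, across N and h |
|---|---|---|---|
| 2% | 0.82 | about 0.84 | 0.05 to 0.14 |
| 5% | 0.68 to 0.69 | about 0.70 | 0.08 to 0.50 |
| 10% | 0.56 | 0.56 to 0.57 | 0.22 to 0.92 |

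Month-0 grouping gives a hazard ratio of 0.97 to 1.01 and type I error of 0.04 to 0.075. Time-dependent status gives 0.97 to 1.01 and 0.035 to 0.08. Simulation error is about √(0.05 × 0.95/600) = 0.009. A repeat of the month-0 analysis with 6,000 runs per setting gave type I error of 0.042 to 0.055, so the 0.075 looks like noise.

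**Cellular testing frequency.** Under the 6.5 table a subject has 5 tests in months 0 to 12 and 2 per year for 4 years: 5 + 8 = 13. If 3-monthly testing continued from the start of year 2, the count would be 5 + 16 = 21, which is the extreme case. With an assumed chance f of a positive per test, P(at least one) = 1 − (1 − f)^n:
- f = 1%: 12% with 13 tests, 19% with 21.
- f = 2%: 23% against 35%.
- f = 5%: 49% against 66%.

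This pushes the opposite way from immortal time, because it adds positives among progressors. The net direction under a grouping that used cellular results is therefore unknown.

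**The case against.** The strongest reply is that the protocol never says it will group on follow-up results. It speaks of a prospective evaluation and schedules antibody at month 0; classifying at entry and following forward is the ordinary reading, and the check above finds it sound. The persistence result belongs to another study, and section 2 also cites a 60% lower risk for positive against negative subjects without a persistence condition. The classification time may well be in an analysis plan that is not at hand. The conversion and event rates are assumed, and at 2% conversion with N = 300 type I error hardly moves.

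Most of this stands. A reader might infer that the planned log-rank test is biased as written; the documents do not support that, because month-0 grouping is compatible with them. A reader might also infer that progressors are tested for antibody more often. They are not: serology is about 3-monthly for everyone. More frequent testing is only implied by 6.5, and only for the additional evaluations from year 2.

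Two things remain. The protocol names a fixed-group test for a marker that it re-measures throughout and expects may change, while nothing in it selects month 0 over later status. And the difference between 6.0 and 6.5 is a contradiction about data collection, which an analysis plan cannot resolve.

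**Conclusion.** The point holds as a conditional risk of moderate severity. With groups set at month 0 there is no immortal time, although confounding is a separate matter that this does not remove. With ever-positive grouping, a marker with no effect would show a rate ratio of about 0.82, 0.68 or 0.56 at 2%, 5% or 10% conversion per year. Type I error would run from about 0.05 to 0.92, depending also on N and event rate. These sizes rest on the assumed rates, 20% positive at entry and no loss of antibody. They apply to ever-positive grouping; a persistent-status rule was not simulated, and its bias would depend on how persistence is defined. No size was computed for the ANOVA.

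The conflict between 6.0 and 6.5 is definite. Its effect is limited to cellular results, where it could touch the frequency and persistence estimates of the primary endpoint. It does not affect antibody-defined groups.

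**What to change.** 1. In 6.6, define the groups for the log-rank test and the ANOVA by anti-Tat antibody status at month 0, with time to AIDS counted from that visit.
2. Use later status only as a time-dependent covariate in a Cox model, with each subject's status carried forward from the previous scheduled visit. Analyse persistence only from a landmark (for example month 12), counting events after it.
3. Estimate frequency and persistence of the cellular response from the visits scheduled for all subjects, and list any progression-triggered samples separately.
4. Reconcile 6.0 with 6.5 on whether the frequency of additional evaluations after year 1 depends on progression.

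The cost is wording and one extra model. No new data are needed.

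### Regimen class is a named stratum and part of the secondary question, but Section 6.6 carries it into neither the CD4 and viral-load ANOVA nor the log-rank test, whose groups are also undefined

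*Protocol*

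**What the plan says.** Regimen class enters the protocol's reasoning in four places.

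- Section 2 states that "it is unknown whether the different class of antiretroviral drugs may play a part in influencing the quality of the immune reconstitution".
- Section 2 later describes the purpose as evaluating the "outcome of anti-Tat positive versus anti-Tat negative patients which are treated by different antiretroviral intervention".
- Section 3.1, under the primary endpoint: "Patients will be stratified according to PI-based or NNRTI-based HAART regimens".
- Section 3.2, the secondary endpoint, concerns "anti-Tat positive versus anti-Tat negative subjects under successful HIV-PI- or NNRTI-HAART in order to define immunologic markers".

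Section 6.6 then lists the analyses.

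- Immune response: "The immune response will be compared between subjects groups stratified by NNRTI-based or PIbased HAART regimens, using a Logistic regression model". This is the only analysis that mentions regimen.
- CD4 and viral load: "compared between anti-Tat positive and negative subjects using an Analysis of variance model (ANOVA". No regimen factor, stratum or interaction is given.
- Time to AIDS: "The time to AIDS will be determined and compared between groups by the Log-Rank test". The groups are not defined and no strata are named.
- Prognostic factors: "A Multivariate analysis will be applied to the immunological and virological parameters in order to carry out potential prognostic factors". Regimen is not among the parameters named.

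Section 3.4 admits subjects on any HAART regimen, so some may belong to neither named class. Section 7.3 has all antiretroviral treatments and changes recorded. Section 6.6 sets no sample size.

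**The concern.** The protocol treats drug class as a possible influence on immunity, names it as a stratum, and mentions it again in the secondary endpoint. Read at face value, the outcome tests make no use of it. Two things could then go wrong with the anti-Tat positive versus negative contrast.

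- **Confounding by regimen.** If anti-Tat positivity differs by class, which is what the logistic model is planned to examine, and class also relates to CD4, viral load or AIDS, a contrast without class carries part of the regimen difference.
- **Averaging over classes.** If anti-Tat status predicts outcome in one class more than in the other, a single contrast gives a value between the two.

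The declared use is a prognostic marker for managing HAART-treated patients. A diluted or confounded estimate could lead to the marker being adopted or dropped across all regimens on evidence that does not show how it behaves in each.

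**Working it through.** The protocol gives no sample size, event count or power, so there is no stated figure to reproduce. The sums below only illustrate how large the two effects could be.

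**Inputs from the protocol (Section 2, as illustrations).** About 20% of asymptomatic infected individuals are anti-Tat antibody positive. A seroconverter cohort showed a 60% lower risk in positives, taken here as a hazard or risk ratio of 0.4. Section 6.6 sets tests at two-sided 5%.

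**Assumed inputs.** Effect 0.4 in one class and 1.0 in the other; the class shares; the risk in negatives; the class sizes; the prevalences by class.

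**1. Averaging.** Pooled log HR ≈ w × ln(0.4) + (1 − w) × ln(1.0), with w the share of information in the affected class.

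| w | pooled HR |
|---|---|
| 0.3 | exp(0.3 × ln 0.4) = 0.76 |
| 0.5 | 0.63 |
| 0.7 | 0.53 |

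On the risk scale with equal baseline risk, pooled RR = 0.4w + 1.0(1 − w), where w is now the affected class's share of subjects: 0.85, 0.70 and 0.55 for w = 0.25, 0.5 and 0.75. A CD4 difference confined to one class appears in the pooled contrast at w times its size.

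**2. Confounding.** Take equal class sizes and anti-Tat prevalence of 15% on PI and 25% on NNRTI.

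- PI share among positives: 0.15 / (0.15 + 0.25) = 0.375.
- PI share among negatives: 0.85 / (0.85 + 0.75) = 0.531.
- Difference: −0.156, so about 16% of any regimen effect on CD4 enters the anti-Tat contrast.

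With prevalences of 10% and 30% the shares are 0.25 and 0.5625, a difference of about 31%. With equal prevalences the leakage is zero.

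**3. Power, effect in one class only.** Two-proportion normal approximation (pooled variance under the null, unpooled under the alternative), 20% positive, 400 subjects per class.

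| Risk in negatives | Pooled, N = 800, RR 0.7 | Affected class, N = 400, RR 0.4 |
|---|---|---|
| 15% | 29% | 58% |
| 5% | 10% | 15% |
| 3% | 7% | 8% |

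At 15% risk and 800 per class the figures are 55% and 91%. At 5% risk and 400 per class, the affected class would expect 80 × 0.05 × 0.4 = 1.6 events among its positives.

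**4. Power, same effect in both classes.** With RR 0.4 throughout, 15% risk and 400 per class, the pooled test has 91% power and each class alone 58%. Splitting loses power here.

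**5. Events.** For 80% power (assumed), d = (1.96 + 0.84)² / (0.2 × 0.8 × (ln 0.4)²), about 59 events within one class at HR 0.4. With an equal split, the interaction (ratio of hazard ratios 0.4) has four times the variance, so it needs about 234 events in total.

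**The case against.** The strongest reply is that the protocol never promises an outcome comparison within each class. The wording in Section 3.2 can describe who is studied. The summary, Section 1 and the opening of Section 3 state the same secondary aim with no mention of class. The stratification sentence stands under the primary endpoint, and the logistic model honours it there. A reader might infer that Section 3.2 poses a by-class question that Section 6.6 then refuses to answer; the text does not establish that.

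A reader might also infer that the plan expressly pools the classes in every outcome test. It does not say so. For the ANOVA, a contrast without regimen is what is written. For the log-rank test the groups are undefined, and the only earlier use of that word in the analysis text refers to the regimen groups. The multivariate analysis is not fully specified either. Model terms and strata may be set in an analysis plan that is not shown.

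The stronger claim that a one-class association will be reported as an average true of neither class also goes too far. Nothing in the protocol says the association differs by class, and the 60% figure comes from seroconverters, not from suppressed patients on HAART. The power advantage of looking within class nearly disappears at low risk and reverses if the association is common to both.

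What remains is narrower. Section 6.6 is not silent on regimen: it names the strata for one analysis and states the others without them, although Section 2 links the outcome comparison to differing treatment. The undefined log-rank groups need correcting on any reading.

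**Conclusion.** The point holds as a specific, inexpensive improvement to Section 6.6. Regimen class is a named stratum and part of the framing of the outcome comparison, yet the ANOVA is stated without it and the log-rank test has neither defined groups nor strata. The consequence is conditional: the contrast is confounded if class relates to both anti-Tat status and outcome, and averaged if the association differs by class. The documents give no figure for either condition.

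Under the assumptions shown, averaging could move a hazard ratio of 0.4 to between 0.53 and 0.76, and regimen imbalance could pass 0% to 31% of a regimen effect into the anti-Tat contrast. The power figures are illustrations under assumed risks and do not show that within-class testing would perform better in this study.

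**What to change.** In Section 6.6:

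- Define the log-rank groups as anti-Tat positive versus anti-Tat negative.
- Stratify that test by regimen class at month 0: PI, NNRTI, other. The third level is needed because any HAART regimen is eligible.
- Include regimen class as a factor in the CD4 and viral-load models.
- Report the anti-Tat contrast for CD4, viral load and time to AIDS within PI and within NNRTI, each with a 95% CI and labelled exploratory. Stratifying or adjusting alone deals with imbalance but still gives one averaged contrast, so the within-class estimates are what would show a difference.
- If an anti-Tat by regimen interaction is estimated, give it with its 95% CI and state that a non-significant result does not show that the classes agree.

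The cost is analysis wording only, since antiretroviral treatment is already recorded. The drawbacks are wider intervals within each class, an interaction of low power, and little gain if AIDS events are few.
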